8.3 Statistical methods

The statistical plan for this study was designed with the assistance of [name] with Penn State Public Health Sciences. The primary end point is the rate (proportion of patients) of local recurrent or residual neoplasia at 6 months for the Hybrid Argon Plasma Coagulation (APC) assisted EMR. Estimate of this recurrent rate will provided with 95% exact binomial confidence limits, which will then be compared to the historical rate of 15-20% recurrent rate for EMR alone. Statistical significance will be declared if the upper limit is smaller than 15%. Even when significance is not reached, the confidence interval provides the plausible range of the local recurrent rate of the APC assisted EMR and helps to decide if a future study with a larger sample size is warranted.

Summary statistics such as percentage of male/female patients, percentage of polyps within the different location of colon, mean diameter of polyps, percentage rate of neoplasia recurrence after 6 months, the percentage of each type of Polyps (Ip, Ila, I Ib, I Ic, etc), and Percentage of successful resection will also be provided. SPSS 22 statistical software shall be used to perform statistical analysis.

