1.3 Secondary Study Endpoints

Evaluate rate of post-polypectomy bleeding and post-polypectomy syndrome and compare it to standard procedure.

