2.0 Background

2.1 Scientific Background and Gaps

Colon Cancer is a major disease that effecting more than 1 million people per year globally. Adenomatous polyps have been identified as the main precursor in lesions leading to colorectal cancer.¹ Colon cancer screening the best way to detect and remove large, often asymptomatic polyps. Early detection and resection of these colorectal polyps can prevent the development of colon cancer. Endoscopic polypectomy introduced in 1970's, is an effective technique to prevent of colorectal cancer, as demonstrated in National Polyps Study. Endoscipc mucosal resection (EMR) is a technique used for resection of medium to large colon polyps. In this technique, fluid is injected into the submucosal creating a cushion between the mucosa and the muscularis propria. An electrocautery snare is then deployed to resect the polyp in a single (en-bloc) or multiple (piecemeal) pieces. Most of polyps > 2cm are resected in piecemeal way. Although EMR is now considered standard of care with successful rate resection of 85 % and low risk of complication (3-10% bleeding and 1% perforation), this technique has inherent deficiencies, especially piecemeal EMR. This is particularly important if the polyp contains cancer. Resection of scarred polyps using this technique is particularly challenging due to the non-lifting of the polyp. Recurrence rates following piecemeal EMR can be as high as 20%.^{1,2} Endoscopic submucosal dissection (ESD) is an alternative approach that aims to remove non-pedunculated precancerous or cancerous lesions over 20 mm in one piece (en-bloc resection rate of 89.95% and lesion recurrence rate of 0.7%). However, due to its technical complexity and high complication risk (mainly bleeding and perforation, with complication rates approximately 8%), it is not the current standard of care and only performed by experts in the technique.¹ Hybrid Argon plasma coagulation (APC) is a new technique in which the endoscopist reinjects the submucosal with fluid to create a cushion (normal saline/ diluted adrenaline and /or sodium hyaluronate solution) to protect the muscle layer and is then ablated using spray argon coagulation to treat any microscopic residual disease that is the seed for local recurrence .³ Previous studies have shown that this technique is a safe and easily applicable technique to complete resection for recurrent polyps after first EMR.

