2.3 Study Rationale

EMR has a recurrence rate of up to 20% in large ≥ 20 mm lesions with a relatively low risk profile. ESD has a low 1-4% recurrence rate but higher risk profile. We are assessing if adjuvant hybrid APC with EMR drop the recurrence rate near ESD levels while maintaining the safety profile of EMR.

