6.2.1.2 Plan to destroy identifiers or a justification for retaining identifiers

Not applicable

6.2.2 Explanation for why the research could not practicably be conducted without access to and use of PHI

The information to be gathered is just for the recruitment purpose. Without it the PI could not identify the eligible subjects. This partial waiver is only for recognize the eligibility of study subjects. Obtaining consent from every subjects come for EMR would be prohibitive, resource exhaustive, and potentially cause confidentiality issues for the ones not be eligible for the study.

6.2.3 Explanation for why the research could not practicably be conducted without the waiver or alteration of authorization

The projects requires look at medical records to identify eligible subjects. Obtaining consent from every subjects come for EMR would be prohibitive, resource exhaustive, and potentially cause confidentiality issues for the ones not be eligible for the study.

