7.2.2 EXAMPLE: Visit 2 or Day 2 or Post-test, etc. (format accordingly)

A follow-up colonoscopy will be scheduled 6 months following the EMR procedure to evaluate for any recurrent polyp.

This is a standard of care for resection of large polyps

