16.2 Feasibility of recruiting the required number of subjects

A total of 40 patients are needed for this study. Approximately, 170 colonic EMR performed at Hershey medical center per year. 100-125 of these EMR are done to remove polyps >2cm. We anticipate complete enrollment in 6 months.

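### Does the unsourced 15% benchmark for EMR alone in section 8.3 call for a local historical control?

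*Combined protocol and SAP*

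**What the plan says.** Section 1.1 hypothesises that Hybrid APC-assisted EMR is more effective than standard EMR. Section 7.1 describes one treated group and no control. The link between the two is in section 8.3: the recurrence rate is reported with exact 95% limits, "which will then be compared to the historical rate of 15-20% recurrent rate for EMR alone", and the result is significant if the upper limit lies under 15%. Section 8.2 assumes 5% recurrence with APC, tests against 15% one-sided with 40 patients, and calls the study a pilot.

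The background supplies a ceiling only. Section 2.1 states: "Recurrence rates following piecemeal EMR can be as high as 20"%. Section 2.3 states: "EMR has a recurrence rate of up to 20% in large ≥ 20 mm lesions". Neither gives a lower figure, and the meta-analysis summary in section 2.2 reports no recurrence rate for EMR.

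On local data, section 16.2 says of the site's yearly EMR volume: "100-125 of these EMR are done to remove polyps >2cm". Section 7.2.2 says of the 6-month colonoscopy: "This is a standard of care for resection of large polyps". Section 1.3 sets a secondary aim: "Evaluate rate of post-polypectomy bleeding and post-polypectomy syndrome and compare it to standard procedure".

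**The concern.** With no control arm, a significant result shows only that recurrence is under 15%. Reading that as superiority over standard EMR requires EMR alone, in these patients at this site, to recur at about 15%. As an EMR recurrence rate, that figure appears only in section 8 and without a citation, while a phrase such as up to 20% also allows 10% or 12%. If the true rate were that low, an ineffective adjunct would be declared significant more often than the 2.5% that two-sided 95% limits imply.

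The site appears to hold data that could test the benchmark: 100 to 125 relevant resections a year, followed by routine 6-month colonoscopy. The plan uses the volume only to show that recruitment is feasible. The natural suggestion is to extract past EMR-alone cases and let the superiority claim depend on a comparison with them.

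**Working it through.** **Inputs.** n = 40, null rate 15%, assumed rate 5%, stated power 60% (section 8.2); exact 95% limits and the 15% threshold (section 8.3); 100-125 resections a year (section 16.2).

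**The plan's own figure.** Section 8.2 states no alpha. The normal approximation at one-sided 0.05 gives

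z = (0.15 − 0.05 − 1.645 × √(0.15 × 0.85/40)) / √(0.05 × 0.95/40) = (0.10 − 0.0929)/0.0345 = 0.207,

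so power is 58.2%, close to the stated 60%.

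**The decision rule.** Two-sided 95% exact (Clopper-Pearson) upper limits:

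| Recurrences | Upper limit |
|---|---|
| 0/40 | 8.8% |
| 1/40 | 13.2% |
| 2/40 | 16.9% |

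The rule is therefore at most 1 recurrence in 40. Its exact power at a true 5% is 39.9%. How that fits with the stated 60% is a separate matter.

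**Error if APC adds nothing and EMR alone recurs at rate r.**

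P(X ≤ 1) = (1 − r)^40 + 40 r (1 − r)^39. At r = 15%: 0.0015 + 0.0106 = 0.0121.

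| EMR-alone rate r | Chance of significance |
|---|---|
| 20% | 0.15% |
| 15% | 1.2% |
| 13.2% | 2.5% |
| 12% (assumed) | 3.9% |
| 10% (assumed) | 8.0% |

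Solving P(X ≤ 1) = 0.025 gives r = 13.16%, which is also the upper limit for 1/40. The rule keeps its nominal error throughout the stated 15-20% and a little below it.

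**What a local control would do.** Assume that 60-90% of past cases qualify and have a 6-month colonoscopy. One year then yields 100 × 0.6 = 60 to 125 × 0.9 = 112 cases, and two years 120 to 225. Suppose the local rate is 15%, so the benchmark is right, and 1/40 is compared with it by a two-sided Fisher test, local events being rounded to the nearest whole number. Over every local size from 60 to 225:

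- p runs from 0.029 to 0.084. At 9/60 it is 0.047, at 15/100 it is 0.040, but at 12/80 it is 0.058.
- p exceeds 0.05 at 27 or 28 of the 166 sizes, depending on how halves are rounded. Of these, 23 lie among the 53 sizes from 60 to 112, the one-year yield.

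The second step can thus withhold the claim although the local data confirm the benchmark exactly.

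Chance of passing both steps at a true 5% with APC, for local sizes 60 to 225 in steps of 5:

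| EMR-alone rate | Present rule | With local gate |
|---|---|---|
| 15% | 39.9% | 21.4-31.8% |
| 20% | 39.9% | 33.5-39.7% |

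With no APC effect and EMR alone at 10%, 12% or 15%, the gated error is 0.5-1.5%, well under the 2.5% it was meant to protect.

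**The case for a change.** The strongest argument for a change is that calling 15% the cautious end of 15-20% helps only if the range has a source. The tolerance is also thin: 13.2% is less than two points below 15%. If the limit is read as one-sided 95%, following section 8.2, 2/40 also passes (upper limit 14.9%) and the tolerance vanishes: the error is 4.9% at 15%, 12.6% at 12% and 22.3% at 10%. Sections 1.1 and 1.3 do promise comparisons with standard EMR, pilot or not.

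The dependence on the benchmark stands, as it does for any single-arm design. The rest is weaker.

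- Every inflated error rate needs an EMR-alone rate that the documents do not give. Section 2.1 cites two references for its ceiling, and they cannot be read here. A missing citation is what can be shown.
- The two background statements do not conflict. Section 2.1 adds that most polyps over 2 cm are removed piecemeal, so a ceiling for piecemeal EMR and one for lesions of 20 mm or more can both be 20%.
- A pooled rate below 15% can be built from the 34.9% en-bloc share in section 2.2, piecemeal recurrence at 20%, and en-bloc recurrence of 0.7-4% borrowed from ESD (sections 2.1 and 2.3): 0.651 × 20% + 0.349 × 0.7% = 13.3%, up to 14.4% with 4%. The borrowing has no support in the documents, and even these values lie above 13.2%.
- For the secondary aim, bleeding figures for EMR are given: 3-10% in section 2.1 and 2.9% in section 2.2. Only post-polypectomy syndrome lacks one, and a descriptive comparison needs no test.
- A retrospective control has its own biases: less uniform follow-up, past cases given APC to be left out, and a usable share that is a guess. It would need review of roughly 100-250 charts and an amendment, since section 6.2.2 limits the present waiver: "This partial waiver is only for recognize the eligibility of study subjects".

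**Conclusion.** No change to the plan follows. The observation is correct: the 15-20% in section 8.3 has no stated source, and the background gives only a 20% ceiling. That is a gap in detail which authors fill when they report, by naming the source of the benchmark and describing a significant result as recurrence under 15%. The analysis itself would be the same.

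The test uses the low, and so the cautious, end of the stated range. Under two-sided limits with all 40 patients evaluated, the error is 1.2% at 15% and stays within 2.5% down to 13.2%. It exceeds that only at rates that have to be assumed. Section 8.3 also says the interval will inform whether a larger study is warranted, which fits a pilot.

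A gating local comparison is a debatable trade. It would protect against a low local rate, but if 15% is right it would remove between about a fifth (39.9% to 31.8%) and nearly half (39.9% to 21.4%) of the chance of the superiority claim, on data of uncertain quality. Descriptive local figures would change no result. The conclusion rests on the two-sided reading of the limits in section 8.3; under a one-sided reading the tolerance is smaller, but the benchmark is no better or worse supported.

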9.0 Confidentiality, Privacy and Data Management

See the Research Data Plan Review Form

9.1 Confidentiality

9.1.1 Identifiers associated with data and/or specimens

9.1.1.1 Use of Codes, Master List

9.1.2 Storage of Data and/or Specimens

9.1.3 Access to Data and/or Specimens

9.1.4 Transferring Data and/or Specimens

9.2 Subject Privacy

10.0 Data and Safety Monitoring Plan

10.1 Periodic evaluation of data

The study involves minimal risk to subjects as it involves evaluate Hybrid APC assisted EMR, which is FDA approved equipment and standard care procedure in U.S. for resection of large polyps.

Oversight for the conduct of the study will be provided by the PI, [name] and the clinical research associate. Any adverse event may occurring will

be documented and reported according to HSPO policies and procedures. The principal investigator and co-investigators will be responsible for data collection and verification, and review of cumulative adverse events. Confidentiality will be protected by utilizing a code number as the only identifier for each subject and the master list will be kept under lock and key with access limited to the PI and research associate. Cumulative adverse events and study progress summary will be communicated to the IRB at the time of continuing review.

10.2 Data that are reviewed

All adverse events will be documented and entered into the Redcap® data management system for centralized data storage and documentation. The following information will be entered: adverse event type, onset/resolution date and time, intensity/severity, action taken, and outcome. All deaths on the study, not related to progression of underlying disease will be reported to the IRB immediately. All unanticipated AE's related or possibly related to study will be reported by PI to the IRB according to HSPO policies and procedures.

10.3 Method of collection of safety information

Patient demographics, risk factors, EMR procedural elements, Pathology results, complications, and all follow up data will be entered into the Redcap® data management system for centralized data storage and documentation.

10.4 Frequency of data collection

Data will be collected at the time of enrollment, the initial procedure, 30 days post procedure phone call (adverse events), 2-3 weeks post-procedure pathology results and 6 month follow-up colonoscopy examination .

10.5 Individuals reviewing the data

The PI and clinical research associate will review cumulative adverse events and accrual every 3 months and report any issues requiring modification of the study or alternation of the risk: benefit ratio to IRB immediately. A summary of adverse events, study progress and protocol modification will be included for IRB review in the continuing progress report.

10.6 Frequency of review of cumulative data

The PI and the clinical research associate will review cumulative adverse events and accrual every 3 months.

10.7 Statistical tests

Not applicable

10.8 Suspension of research

The study team will make decisions regarding cessation of accrual. This trial will be suspended for review for any patient death during, or up to 30 days after participating in the trial if felt to be causally related to participation in this trial. The study team and the Office of Human Protection will then decide after review whether it is safe to continue the trial.

11.0 Risks

The research involves no more than minimal risk to participants because it involves prospective review of the patient's medical records, procedure details and any adverse events may occur for limited and in-sensitive

information. The only risk is the loss of patient confidentiality and the risk will be minimized by coding the research data and keeping separate list that links code number with identifiers.

12.0 Potential Benefits to Subjects and Others

12.1 Potential Benefits to Subjects

There are no guarantees that subjects will benefit from participating in a research study, however, we hope there is a benefit of reducing recurrence rate while maintaining safety.

12.2 Potential Benefits to Others

The results of this research may lead to a technique for better way of complete resection of large polyps and safer one for future patients.

13.0 Sharing Results with Subjects

Data and results of the study outcome will not be shared with either the patient, primary provider, or referring provider. The results of the colonoscopy will be shared as per normal routine of the endoscopist.

14.0 Subject Stipend (Compensation) and/or Travel Reimbursements

Not Applicable

15.0 Economic Burden to Subjects

15.1 Costs

Participant will not bear any costs which are not part of standard care.

15.2 Compensation for research-related injury

Subjects will not receive any compensation for being in this research study. As this is a low risk study, the like-hood of complications or injury is very small. Is it possible however, that the subject could develop complications or injuries as a result of participating in this research study. In the event of injury resulting from this research, medical treatment is available but will provide at the usual charge.

It is the policy of the institution to provide neither financial compensation nor free medical treatment for research-related injury. In the event of injury resulting from this research, medical treatment is available but will be provided at the usual charge. Costs for the treatment of research-related injuries will be charged to subjects or their insurance carriers.

16.0 Resources Available

16.1 Facilities and locations

All study procedures including colonoscopy will be conducted at Gastrointestinal Endoscopy and Motility Center at UPS (suite 2000) at Hershey Medical Center. The fully-staffed Gastrointestinal Endoscopy and Motility Center features 8 endoscopy rooms with state of the art Olympus endoscopes. Two of the room designed to accommodate advanced therapeutic procedures, and have fluoroscopic capabilities. The suite has several onsite anesthesiologists, nurses and physicians. Measures in place to maintain patient privacy include: procedures that are performed in private studios or rooms and recovery that occurs in curtained rooms. If required, continuous emergency care is available. The primary investigator [name] is an Assistant Professor of Medicine. He has extensive experience with colonoscopy and EMR procedures. Additionally [name] has several years of research experience as PI or Co-Investigator.

16.2 Feasibility of recruiting the required number of subjects

A total of 40 patients are needed for this study. Approximately, 170 colonic EMR performed at Hershey medical center per year. 100-125 of these EMR are done to remove polyps >2cm. We anticipate complete enrollment in 6 months.

16.3 PI Time devoted to conducting the research

As the principal investigator, [name] has devoted a set amount of time to oversee the administration and surveillance of this study and to perform the procedures. He has been given a dedicated amount of academic time to pursue research, and while limited, it is sufficient to oversee and execute this trial safely and effectively.

16.4 Availability of medical or psychological resources

Patients will have continuous monitoring of vital signs during and after the colonoscopy procedure as is standard of care for this procedure as outlined in the protocol. Continuous emergency medical care is available for any patient undergoing colonoscopy and to this study population as standard of care. Physician, nursing, and support staff are available continuously while the patient is in the endoscopy suite.

16.5 Process for informing Study Team

The study team will meet to review the study procedures every month at the therapeutic pod meeting. All team members will be up to date on the progress of the study and any adverse events that may occur.

17.0 Other Approvals

17.1 Other Approvals from External Entities

Not applicable

17.2 Internal PSU Committee Approvals

Check all that apply:

Anatomic Pathology – Hershey only – Research involves the collection of tissues or use of pathologic specimens. Upload a copy of HRP-902 - Human Tissue For Research Form on the “Supporting Documents” page in CATS IRB. This form is available in the CATS IRB Library.

- Animal Care and Use – All campuses – Human research involves animals and humans or the use of human tissues in animals
- Biosafety – All campuses – Research involves biohazardous materials (human biological specimens in a PSU research lab, biological toxins, carcinogens, infectious agents, recombinant viruses or DNA or gene therapy).
- Clinical Laboratories – Hershey only – Collection, processing and/or storage of extra tubes of body fluid specimens for research purposes by the Clinical Laboratories; and/or use of body fluids that had been collected for clinical purposes, but are no longer needed for clinical use. Upload a copy of HRP-901 - Human Body Fluids for Research Form on the “Supporting Documents” page in CATS IRB. This form is available in the CATS IRB Library.
- Clinical Research Center (CRC) Advisory Committee– All campuses – Research involves the use of CRC services in any way.
- Conflict of Interest Review – All campuses – Research has one or more of study team members indicated as having a financial interest.
- Radiation Safety – Hershey only – Research involves research-related radiation procedures. All research involving radiation procedures (standard of care and/or research-related) must upload a copy of HRP-903 - Radiation Review Form on the “Supporting Documents” page in CATS IRB. This form is available in the CATS IRB Library.
- IND/IDE Audit – All campuses – Research in which the PSU researcher holds the IND or IDE or intends to hold the IND or IDE.
- Scientific Review – Hershey only – All investigator-written research studies requiring review by the convened IRB must provide documentation of scientific review with the IRB submission. The scientific review requirement may be fulfilled by one of the following: (1) external peer-review process; (2) department/institute scientific review committee; or (3) scientific review by the Clinical Research Center Advisory committee. NOTE: Review by the Penn State Hershey Cancer Institute Scientific Review Committee is required if the study involves cancer prevention studies or cancer patients, records and/or tissues. For more information about this requirement see the IRB website at: <http://www.pennstatehershey.org/web/irb/home/resources/investigator>

